Cover Page:

Personalized Integrated Chronotherapy for Perinatal Depression
Uploaded: October 24, 2025

NCT04364646

Protocol version: 03/20/2023

Background:

Increasing evidence suggests a connection between mood disorders and circadian dysfunction, or dysfunction of the ‘internal body clock’ that helps regulate 24-hour cycles of sleep and wakefulness.¹ Integrated chronotherapy is a treatment approach that integrates bright light therapy, an advance in timing of the sleep-wake schedule, sleep schedule stabilization, and sleep scheduling, to address circadian dysfunction and thus ameliorate symptoms of mood disorders.² Chronotherapy has been used and established as an effective treatment for patients with unipolar^{3,4} and bipolar⁵⁻⁹ depression outside of the perinatal period.²

This multi-site study aims to assess the efficacy of personalized, integrated chronotherapy (PIC) in treating perinatal depression with or without concomitant anxiety. We hypothesize that women who suffer from depression/anxiety during their third trimester who receive PIC in addition to usual care (UC), (in comparison to women who receive UC only), will show improvement in depressive and anxiety symptoms throughout the remainder of their pregnancy into the postpartum period. Secondary hypotheses are that the women receiving PIC along with UC will in fact demonstrate changes to their circadian rhythms, and that these changes will mediate, or explain, any improvements in depression and anxiety symptoms.

This R01 study aims to recruit 220 women across 5 sites to complete at least 176 participants. (This will accommodate a 20% screening failure and attrition rate.) Women with major depression will be recruited in the third trimester of pregnancy as verified by diagnostic measures. Subjects will be randomly assigned to UC or PIC+UC. PIC will entail that the subjects use a bright light box to expose themselves to light for 15-60 30 minutes each morning, follow an individualized sleep/wake schedule, keep a sleep/wake journal, and wear an actigraph (a wrist device resembling a wristwatch) to measure activity and light exposure throughout the day. Subjects in both groups will also have seven visits during their study enrollment, which will extend from 24-28 weeks’ gestation to eighteen weeks postpartum; At these visits, subjects will complete self-report measures and participate in mood assessments administered by a blinded clinician, their actigraph data will be downloaded and collected, and their prescribed sleep schedule will be adjusted as needed. At the beginning, middle, and end of the study, subjects will complete a sleep diary as well as provide three sets of saliva samples for evaluation of biological markers of circadian rhythm changes. The aim of this study is to assess the feasibility of integrating PIC into routine clinical care and to test whether the outcome of PIC is beneficial to both mother and infant.

Specific Aims:

Specific Aim 1: Examine the efficacy of PIC, acting through chronobiologic targets, to improve mood in women with major depression during third trimester (N=220). Hypothesis: Compared to women receiving UC for depression during pregnancy, women in the PIC+UC group will show greater improvement in dependent measures of depression (HAMD) and anxiety (HAMA) at pregnancy week 36 and postpartum week 6.

Specific Aim 2: Examine hypothesized mechanisms of change to confirm that PIC engages and alters the RDoC domains targeted by chronotherapy (specifically DLMO, Sleep Onset, Sleep Offset, Phase Angle (PA), Light Levels), and to determine whether changes in targeted domains are associated with antidepressant response. Hypothesis 2a: Compared to UC, PIC+UC patients will have earlier circadian phase and bed/wake times and shorter PA at pregnancy week 36 and postpartum week 6. Hypothesis 2b: Decrease in HAMD and HAMA scores will be mediated by changes in DLMO, sleep onset, sleep offset, phase angle, and light levels.

Exploratory Aims: (a) In 100 mother-infant pairs, examine if maternal DLMO is related to (i) melatonin levels and onset in breastmilk at postpartum week 6, and (ii) infant sleep measured with ankle actigraphy at 18 weeks; (b) Explore factors relevant to future widespread dissemination of perinatal PIC, including health care utilization in UC vs. PIC+UC groups and quality of PIC delivery by different health care providers.

Eligibility Criteria:

The study team intends to enroll 220 subjects, females who are 24 to 28 weeks pregnant at screening and who are seeking treatment for depressive/anxiety symptoms. This time frame was selected for both scientific and practical reasons (i.e., most pregnancies that gestate to this time point are viable, sleep disturbances are common at this stage, it is early enough in pregnancy to have an impact, and the resulting study duration is not a burden for participants). We will include pregnant women aged 18-45 years old inclusive, with a baseline Hamilton Depression Rating Scale (HAMD-17) score ≥ 14 and a current DSM-5 diagnosis of MDD as determined with the Current Major Depressive Episode Module of the Structured Clinical Interview for DSM disorders (SCID-I/P) during the Screening Visit (V1). The rationale for involving the protected population of pregnant women in this study is that we are investigating the utility of a non-pharmacologic antidepressant treatment option in the specific population of perinatal women.

and, therefore, must involve these women in the study. This will allow us to longitudinally gauge the efficacy of Integrated Chronotherapy in reducing perinatal depressive/anxiety symptoms. We will allow women with tobacco dependence to enroll. Furthermore, women's preferred choice of either bottle feeding or breastfeeding will not affect her eligibility. We anticipate some participants will take antidepressant, anxiolytic, and/or mood stabilizing medications as part of usual care (UC). We will allow women who are taking medications to enroll because medication use for mood disorders during pregnancy reflects current medical practice and will improve generalizability. Integrated Chronotherapy as administered through this research study will merely supplement any clinical care women are receiving. However, the team will be mindful to only enroll participants who start an antidepressant before at least four weeks of scheduled Screening Visit. This measure is only to control for any prolonged onset of action that could lead to decreased depressive symptoms due to the antidepressant, rather than the study intervention(s). We will also enroll women who are not taking medications. Our goal is to recruit patients who can participate in the PIC intervention safely and who will be representative of women who present with depression/anxiety during pregnancy.

The following factors will exclude participants from the study: active psychosis or suicidality contraindicating outpatient treatment as determined by the clinical judgement of the research team and as assessed with the B/C module of the SCID-I/P and the Columbia-Suicide Severity Rating Scale (C-SSRS), respectively; bipolar disorder (because sleep restriction can increase risk of conversion to mania); seizure disorder (because sleep restriction can increase seizure risk); self-report of frequent migraines/headaches precipitated by bright light or sleep deprivation; preexisting eye/skin disorders contraindicating light therapy; use of photosensitizing medications; primary Axis I diagnosis other than major depressive disorder (MDD); high risk pregnancy (e.g., conditions requiring mandatory bed rest or complex medical regimens that will interfere with study participation or conditions where poor infant outcomes are anticipated); starting antidepressants within four weeks prior to enrollment (see above); current employment as nightshift worker; Alcohol Use Disorders Identification Test (AUDIT) score ≥ 8 and/or Drug Abuse Screening Test (DAST) > 1 indicating current alcohol or drug use disorders; women whose infants will not be living in the home or who will have a nighttime caregiver; Pittsburgh Sleep Quality Inventory (PSQI) < 5 (i.e., those who report no sleep complaints during third trimester of pregnancy and for whom an intervention targeting sleep might not be indicated; the PSQI has been validated in pregnant women); women who do not speak and read English because PIC research instruments are only available in English at this time. Women who experience fetal loss or stillbirth, as well as mothers whose infants are born before 36 weeks gestation or have NICU stays longer than five days, will be discontinued from the study but will continue to receive UC.

Study Procedures:

Following the initial pre-screening process to ascertain a woman's eligibility, interested participants will be scheduled for Visit 1 (Screening) at 24-28 weeks gestation. The duration of this visit will be up to three hours. Study staff will thoroughly review the informed consent form with subject prior to the initiation of any protocol-specific procedures. If the woman provides her consent, she will be randomized to receive personalized bright light therapy and a prescribed sleep schedule (PIC) in addition to usual care (UC) (i.e. medications, talk therapy, etc.) or usual care (UC) alone. The PIC treatment will include both daily bright light therapy and personalized sleep prescriptions.

Subjects will be required to complete a total of seven study visits as described below. Whenever possible, these visits will place at the research offices at the respective sites. Visits may be performed as virtual visits via telephone and/or video if necessary.

Study Outline			
Visit	Time	Scheduling Window	Measures
Pregnancy Phase			
Visit 1 (Screening, Consenting, and Randomization)	24-28 Weeks Pregnancy	N/A	Screening Interview and Forms
Visit 2 (Baseline)	28-30 Weeks Pregnancy	28 Weeks, 0 Days – 30 Weeks, 6 Days	Home Sleep and Light Monitoring, Mood, Circadian Phase 1
Visit 3	33 Weeks Pregnancy	33 Weeks, 0 Days – 33 Weeks, 6 Days (+/- 6 Days)	Home Sleep and Light Monitoring, Mood
Visit 4	36 Weeks Pregnancy	36 Weeks, 0 Days – 36 Weeks, 6 Days (+/- 6 Days)	Home Sleep and Light Monitoring, Mood, Circadian Phase 2
Postpartum Phase			
Visit 5	2 Weeks Postpartum	2 Weeks, 0 Days Postpartum – 2 Weeks, 6 Days Postpartum	Home Sleep and Light Monitoring, Mood
Visit 6	6 Weeks Postpartum	6 Weeks, 0 Days Postpartum – 6 Weeks, 6 Days Postpartum (+/- 6 Days)	Home Sleep and Light Monitoring, Mood, Circadian Phase 3

Visit 7	18 weeks postpartum	18 weeks, 0 days postpartum to 18 weeks, 6 days postpartum (+/- 6 days)	Home Sleep and Light Monitoring, Mood assessment; debriefing.
---------	---------------------	---	---

Throughout the study treatment (beginning after completing the baseline data collection at Visit 2), women in the PIC+UC group will be asked to sit with a bright light box every morning. The starting prescription is to use the light box for 30 minutes within the first 45-60 minutes after waking. Personalized prescriptions will take into account individual participants' schedules and morning responsibilities. Light duration may be adjusted within the range of 15-60 minutes depending on participant's response. Women will be instructed to use the light every day with the light box positioned approximately 12-24 inches from the eyes. She may be permitted to read, watch TV and do other activities so long as it does not block her eyes from the light. Although the light box therapy has no known adverse effects to newborns, participating women will be instructed not to hold their newborn infants while they are undergoing bright light therapy. Language regarding this is included in the sleep prescription that will be completed by study staff and provided to the participant.

Women will also be specifically prescribed a personalized sleep schedule based on their reported sleep patterns and constraints related to specific schedules.

Continuous sleep and light monitoring through an actigraph will occur to estimate sleep times and light exposure. Women will be instructed to wear the actigraph at all times throughout study enrollment except in instances where it may be damaged (i.e. water exposure while showering/bathing).

On weeks where melatonin saliva sampling is scheduled (baseline, pregnancy week 36 and postpartum week 6, see below), women will complete a daily sleep diary. Once the mother has delivered, the infant's sleep patterns may also be collected on the diary.

A total of three saliva sample sets will be collected as a part of this study at 28 Weeks Gestation, 36 Weeks Gestation and 6 Weeks Postpartum (weeks of Visit 2, 4 and 6). This is to measure melatonin concentrations. Women will be asked to collect twelve saliva samples each evening every half hour at a time that is assigned based on their sleep patterns during the visit week.

Infant assessments will be conducted at Postpartum Week 18, requiring participants to complete questionnaires on their infants' sleep/behavior. Infants will also wear an actigraph on their ankle for one week to obtain an objective measure of sleep patterns.

The 7 study center visits will include downloading of wrist monitor data, examination of sleep and activity data as measured through the actigraph versus what was reported in the sleep diary (during applicable weeks). Treatment sleep schedules will also be assigned and adjusted at study center visits. Questionnaires and blinded clinical assessments will be administered to measure mood, safety measures (e.g. suicidality and manic symptoms).

Analytic Strategy Registered with AsPredicted.org

1) Data collection:

Have any data been collected for this study already?

It's complicated. We have already collected some data but explain in Question 8 why readers may consider this a valid pre-registration nevertheless.

(Note: Choices are 'Yes, we already collected the data.', 'No, no data have been collected for this study yet.' and the answer above. Also, 'Yes' is not an accepted answer.)

2) Hypothesis:

What's the main question being asked or hypothesis being tested in this study?

The primary aim of this single-blinded RCT is to test whether adding a personalized integrated chronotherapy intervention (PIC) to usual care (UC) for perinatal depression improves mood better than UC alone in individuals who meet criteria for major depression during 3rd trimester of pregnancy. Participants are females ages 18-45 years recruited at 24-28 weeks' gestation across 5 study sites. They are enrolled between 28-30 weeks of gestation and take part in the study through postpartum week 18. After the screening and consenting visit (V1), they are randomized to UC or PIC+UC and have 6 more study visits: baseline (V2), gestational week 33 (V3), gestational week 36 (V4), postpartum week 2 (V5), postpartum week 6 (V6) and postpartum week 18 (V7). Sleep and mood are measured at Visits 2-7 and dim light melatonin onset is measured at Visits 2, 4, and 6.

Hypothesis: Compared to women receiving UC for depression during pregnancy, women in the PIC+UC group will show greater improvement in dependent measures of depression (HAMD) at postpartum week 6

3) Dependent variable:

Describe the key dependent variable(s) specifying how they will be measured.

The primary dependent variable is the score on the Hamilton Depression Rating Scale (HAMD-17) which is evaluated by blinded raters at the end of each study week. We are also measuring the Hamilton Anxiety Rating Scale (HAMA).

4) Conditions:**How many and which conditions will participants be assigned to?**

Participants are randomized to usual care (UC) or personalized integrated chronotherapy (PIC)+UC. We are using urn randomization to allocate women to UC or PIC+UC while balancing for expectant mothers' parity and whether women self-identify as declining pharmacologic treatment for perinatal depression.

5) Analyses:**Specify exactly which analyses you will conduct to examine the main question/hypothesis.**

Changes in HAMD from baseline will be compared using generalized estimating equations, treating follow-up points as discrete time points, having correlated error within patient. All study time points will be in the model, but our main hypothesis will be tested as an interaction involving the baseline time point and postpartum week 6. This will be carried out within the model using orthogonal linear contrasts. Distributions for each dependent variable will be based on: a) real-world constraints, and b) model residual diagnostics. We will adjust for additional model misspecification using classical sandwich estimation.

6) Outliers and Exclusions**Describe exactly how outliers will be defined and handled, and your precise rule(s) for excluding observations.**

We will identify a data point as an outlier that should be excluded only if the value is impossible/implausible biologically or if there is corroborating evidence independent of the observation value that indicated a protocol deviation or concern related to data collection.

7) Sample Size How many observations will be collected or what will determine sample size? No need to justify decision, but be precise about exactly how the number will be determined.

We will continue enrolling through April 2024 and accept the sample size accrued at that point.

8) Other Anything else you would like to pre-register?

(e.g., secondary analyses, variables collected for exploratory purposes, unusual analyses planned?)

The official start date of this study was 02/02/2020. Required COVID restrictions and the relocation of one of our study sites limited participant recruitment. Thus, we have changed our analytic strategy. Our original plan was to conduct an interim two-tailed analysis after 100 participants completed the study to test for early signs of confirmatory efficacy, with the plan to switch all patients to PIC+UC if the HAMD reduction between groups was significantly different at alpha=0.005 either at 36 weeks of pregnancy or 6 weeks postpartum. Absent that, we planned to use two-tailed tests of the HAMD change using an alpha of 0.02 at 36 weeks of gestation and 6 weeks postpartum. To avoid an underpowered study, we will now test a one-tailed hypothesis at 6 weeks postpartum. We are therefore registering our one-tailed hypothesis while we are still enrolling participants and collecting data to establish our new *a priori* analytic plan.

Our secondary aim is to examine putative mechanisms of change to confirm that PIC engages and alters the RDoC domains targeted by chronotherapy (specifically DLMO, Sleep Onset, Sleep Offset, Phase Angle (PA), and Light Levels) and to determine whether changes in targeted domains are associated with antidepressant response. For this aim, we hypothesize that (a) compared to UC, PIC+UC patients will have earlier circadian phase and bed/wake times and shorter PA at pregnancy week 36 and postpartum week 6; and (b) decrease in HAMD scores will be mediated by the changes in DLMO, Sleep Onset, Sleep Offset, Phase Angle, and Light Levels.

9) Name

Give a title for this AsPredicted pre-registration

Personalized Integrated Chronotherapy for Perinatal Depression NCT04364646

10) Type of study

Experiment

11) Data source

Field experiment / RCT

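### Women are randomized at V1, but the HAMD that anchors the primary contrast is taken 0 to 48 days later at V2, and the plan does not say when allocation is disclosed

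*Combined protocol and SAP*

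**What the plan says.** **Order of events.** The Study Outline table labels the first visit "Visit 1 (Screening, Consenting, and Randomization" and places it at 24-28 weeks. V2, at 28w0d to 30w6d, is the Baseline visit. Analytic Strategy item 2 gives the same order: "After the screening and consenting visit (V1), they are randomized to UC or PIC+UC and have 6 more study visits: baseline (V2".

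**Primary test.** Item 5 states that "our main hypothesis will be tested as an interaction involving the baseline time point and postpartum week 6". Item 2 lists mood at Visits 2 to 7 only, so the first HAMD in the model is the one at V2.

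**Start of treatment.** Study Procedures introduces the light-box instructions with "Throughout the study treatment (beginning after completing the baseline data collection at Visit 2". PIC therefore follows the V2 data collection.

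**Blinding.** Item 2 opens with "The primary aim of this single-blinded RCT", and item 3 says that the HAMD is "evaluated by blinded raters at the end of each study week". The Background also mentions a blinded clinician. Nothing describes participants or treating staff as blinded, and nothing says when either learns the allocation.

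**Related wording.** Eligibility Criteria applies the HAMD threshold of 14 to a *baseline* score, in a sentence that ends with the Screening Visit. It also says the team will "only enroll participants who start an antidepressant before at least four weeks of scheduled Screening Visit", and gives as the reason "to control for any prolonged onset of action that could lead to decreased depressive symptoms due to the antidepressant". The exclusion list counts the same four weeks back from enrollment, and item 2 puts enrollment at 28-30 weeks.

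**The concern.** Randomization makes the arms comparable in expectation at the moment of allocation. A score taken later is comparable only if nothing related to allocation has acted on it in between. Three things could act between V1 and V2 if allocation is known:

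- **Expectancy.** The HAMD is scored by a blinded rater, but from what the woman says. A woman who knows she will receive PIC, or knows she will not, may answer differently.
- **Usual care.** Women or their clinicians may change medication or talk therapy because of the assignment.
- **Loss.** A woman lost between V1 and V2 contributes no HAMD to the model. The 20% allowance in the Background combines screening failure with attrition, so such losses are not identified, overall or by arm.

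The primary contrast subtracts the V2 arm difference from the week 6 arm difference, so any arm-related shift at V2 enters the main result directly. Since PIC starts only after V2 collection, nothing stated in the plan requires allocation to be made, or known, before then.

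**Working it through.** **1. The gap.** The documents give no V1-to-V2 interval, so there is no stated figure to reproduce. From the visit windows, in days of gestation:

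- Earliest V1: 24w0d = 7 × 24 = 168.
- Latest V1: 28w0d = 196 (or 28w6d = 202, if the whole of week 28 counts).
- V2 window: 28w0d = 196 to 30w6d = 7 × 30 + 6 = 216.
- Maximum gap: 216 - 168 = 48 days.
- Minimum gap: 0 days, because the windows meet at 28w0d (or overlap to 28w6d).
- Between window midpoints: 206 - 182 = 24 days (206 - 185 = 21 if V1 runs to 28w6d).

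A woman seen at 24w0d waits 28 to 48 days; at 26w0d, 14 to 34; at 28w0d, 0 to 20. If randomization follows V1 by some days, as item 2 could be read, the gap is shorter.

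**2. Effect on the contrast.** Let b be the PIC+UC minus UC difference in V2 HAMD caused by allocation, c the fraction of it that persists to week 6, and T the week 6 difference that would arise without it.

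- Week 6 arm difference: T + cb. This is the effect of assignment.
- Planned change contrast: (T + cb) - b = T - (1-c)b.

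So b moves the planned contrast by -(1-c)b from T. It misses the effect of assignment by -b, whatever c is.

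**3. Illustration.** T = -2 and b = ±1 are assumptions; the documents give neither.

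| b | c | planned contrast | week 6 difference |
|---|---|---|---|
| -1 | 0 | -1.0 | -2.0 |
| -1 | 0.5 | -1.5 | -2.5 |
| -1 | 1 | -2.0 | -3.0 |
| +1 | 0 | -3.0 | -2.0 |
| +1 | 0.5 | -2.5 | -1.5 |
| +1 | 1 | -2.0 | -1.0 |

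**4. Would a check of V2 balance settle it?** The 95% half-width for the V2 arm difference with equal arms is 1.96 × SD × 2/√N. N = 176 is the completer target in the Background. N = 100 is assumed, because item 7 accepts whatever accrues. SD 4 to 6 is assumed.

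- N = 176: 1.18 (SD 4), 1.48 (SD 5), 1.77 (SD 6).
- N = 100: 1.57, 1.96, 2.35.

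A by-arm table of V2 HAMD is worth having, but it would leave shifts of one to two points unresolved.

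**5. Precision of a V1-adjusted analysis.** Compared with adjustment for V2, the SE ratio is √((1-r₁²)/(1-r₂²)), where r₁ and r₂ are the correlations of V1 and V2 HAMD with week 6. At assumed pairs (0.2, 0.3), (0.3, 0.5) and (0.5, 0.7) it is 1.03, 1.10 and 1.21.

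**The case against.** The strongest reply is that allocation at V1 is not disclosure at V1. Treatment waits for V2 and the raters are blinded. If women and treating staff do not learn the assignment early, b has no source. That stands: a reader might infer that women were told at V1, but the documents are silent, and silence does not show it.

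Three further points also stand:

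- The most natural expectancy effects (hope in PIC+UC, disappointment in UC) both make b negative. That pulls the contrast toward zero and is conservative for the one-tailed test. Allocation-driven changes in usual care or losses could go either way, so the direction remains open.
- It is tempting to say that antidepressant starts between V1 and V2 escape the four-week rule. That holds only when the rule is counted from the Screening Visit. Counted from an enrollment at 28-30 weeks, most such starts would fall inside it. Starts also matter here only if they differ by arm. The urn balances on declining pharmacologic treatment, which limits chance imbalance but would not prevent starts prompted by allocation.
- A reader might conclude that no available analysis is free of bias. For the effect of assignment, that is wrong. A week 6 comparison adjusted for a pre-randomization HAMD is protected by randomization, apart from missing data. It looks biased by cb only if persisting expectancy is defined as outside the effect of interest. Withholding allocation until V2 would not remove expectancy that begins later.

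None of this answers the point that the anchor of the primary contrast is measured after randomization with no stated safeguard on disclosure.

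**Conclusion.** The point holds as a weakness in procedure that is cheap to remove. Randomization at V1, the V2 anchor, the 0 to 48 day range and the absence of any statement on disclosure all come directly from the documents. Whether the contrast is affected depends on allocation being known before V2 and on b, whose size the documents do not give. The illustrated effects and half-widths rest on assumed values, and no error rate is claimed.

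The documents do not support saying that the primary result is biased, or in which direction. Nor do they establish that a V1 HAMD exists to adjust for. The eligibility sentence may attach the Screening Visit only to the diagnostic interview, the Study Outline lists only a screening interview and forms at V1, and item 2 starts mood measurement at V2.

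**What to change.** **Women not yet randomized.** Either run the urn randomization once V2 baseline collection is complete, or keep it at V1 and withhold the result from participants and treating staff until then. Neither needs an added visit or assessment. Both are mid-trial procedure changes that reach only remaining enrollees. Moving randomization also takes V1-to-V2 losses out of the randomized denominator for later women but not for earlier ones; withholding keeps one denominator.

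**Women already randomized.** Keep the V2 contrast as primary. State when allocation was disclosed, and report by arm the V2 HAMD, losses between V1 and V2, and usual-care changes in that interval, including antidepressant starts. If enrollment closed as planned in April 2024 (the document was uploaded in October 2025), only this reporting and the sensitivity analysis below remain.

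**Sensitivity analysis, conditional.** If the eligibility HAMD was scored at V1 before randomization, prespecify the week 6 arm difference adjusted for that score, with V2 treated as post-randomization, and read it beside the primary contrast. Its SE would be about 3% to 21% larger than with V2 adjustment under the assumed correlations. It does not supply outcomes for women lost before V2.

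**Wording.** Name the visit meant by *baseline* in Eligibility Criteria, the Study Outline and items 2 and 5. Reconcile the anchor of the four-week antidepressant rule (Screening Visit in one place, enrollment in another) with item 2's placing of enrollment at 28-30 weeks.

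### The registered primary GEE omits both urn balancing factors, which forgoes a little power if they predict HAMD change but does not affect validity

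*Combined protocol and SAP*

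**What the plan says.** Under the heading Analytic Strategy Registered with AsPredicted.org, item 4 (Conditions) describes urn randomization to the two arms, balanced on "parity and whether women self-identify as declining pharmacologic treatment for perinatal depression".

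Item 5 (Analyses) asks for an exact specification. It answers that "Changes in HAMD from baseline will be compared using generalized estimating equations", with visits as discrete time points and correlated errors within patient, and that "our main hypothesis will be tested as an interaction involving the baseline time point and postpartum week 6". It adds that "We will adjust for additional model misspecification using classical sandwich estimation". That adjustment concerns the variance estimator; it is not covariate adjustment. No covariate is named in item 5, in item 8 or in the protocol text before the registration. The choice of distribution is left to data constraints and residual diagnostics.

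Two other statements bear on how much precision matters. Item 8 gives the reason for the change of test: "To avoid an underpowered study, we will now test a one-tailed hypothesis at 6 weeks postpartum". Item 7 sets the sample size: "We will continue enrolling through April 2024 and accept the sample size accrued at that point".

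**The concern.** When allocation is balanced on a factor that predicts the outcome, the real variability of the arm difference falls, because chance imbalance on that factor is partly removed. A model without the factor still counts its contribution as residual noise, so the standard error does not fall to match. The sandwich estimator does not recover this. The precision that balancing makes available is then partly unused.

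The registered contrast is the change from baseline to postpartum week 6. Only an effect of parity or declining medication on change matters. An effect on the level of HAMD that is the same at every visit cancels out of the contrast.

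What is at stake is some power, in a trial that moved to a one-tailed test for fear of having too little and that fixes its sample by calendar date.

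**Working it through.** **Inputs from the documents.** 220 recruited, at least 176 completers and 20% loss (study overview in the Background); two urn factors (item 4); week 6 change contrast and classical sandwich (item 5); one-tailed test (item 8).

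**Inputs assumed.** One-sided 0.05; 1:1 allocation; identity link; normal critical value; two binary factors (prevalence 0.5 and 0.4) sharing equally an R2 for change of 0, 0.05, 0.10 or 0.20; an urn with one starting ball per arm and one opposite ball added, using the more imbalanced urn.

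**1. The plan's own figure.** 176 / (1 - 0.20) = 220, which reproduces. The documents state no power.

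**2. Effect giving 80% nominal power.** (1.645 + 0.842) x sqrt(2/88) = 2.487 x 0.1508 = 0.375 SD of change.

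**3. What each R2 means.** Each factor's shift in change is sqrt[(R2/2) / (p(1 - p))]. For R2 of 0.05, 0.10 and 0.20 this is 0.316, 0.447 and 0.632 SD at p = 0.5, and 0.323, 0.456 and 0.645 SD at p = 0.4. Those are about 0.85, 1.2 and 1.7 times the assumed treatment effect, so 0.20 is treated as an upper bound.

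**4. Formula, perfect balance.** With adjustment, power is Φ(2.487/√(1 - R2) - 1.645): 81.8, 83.5 and 87.2% at R2 0.05, 0.10 and 0.20. With the factors balanced but omitted, power is Φ(0.842/√(1 - R2)): 80.6, 81.3 and 82.7%. The power forgone is 1.2, 2.2 and 4.5 points, and nil at R2 = 0.

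**5. Simulation with the urn, N = 176, complete data.** 60,000 trials per cell for power; null rejection pools two such runs. With all effects by visit, the GEE contrast equals least squares on change. Kauermann-Carroll (KC) is the corrected sandwich.

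| R2 | Registered: no factors, classical | Factors by visit, KC | Net (points) | Null rejection, registered |
|---|---|---|---|---|
| 0 | 80.3% | 79.9% | -0.4 | 5.2% |
| 0.05 | 80.4% | 81.4% | +1.0 | 4.9% |
| 0.10 | 80.8% | 83.3% | +2.5 | 4.7% |
| 0.20 | 81.7% | 87.0% | +5.3 | 4.2% |

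The urn balances only partly, so the registered test gains less from balance than the formula allows. A separate simulation (6,000 trials per cell) gave 79.4 vs 79.1, 80.0 vs 81.2, 80.5 vs 83.5 and 81.6 vs 86.8%.

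**6. Smaller samples.** Holding nominal power at 80% requires a larger effect: 2.487 x sqrt(2/50) = 0.50 SD at N = 100 and 2.487 x sqrt(2/30) = 0.64 SD at N = 60. On that footing the net change at R2 0, 0.05, 0.10 and 0.20 is -0.7, +0.7, +2.2 and +5.0 points (N = 100), and -1.3, 0, +1.5 and +4.6 (N = 60). If the effect stays at 0.375 SD, power is only about 59% and 43%; the net change at N = 100 is then -0.9, +0.8, +2.4 and +6.8.

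**7. Which terms are needed.** On raw scores with complete data, main effects shift all visits equally and cancel. At R2 0.10 the SD of the contrast was 0.1442 both without factors and with main effects only, and 0.1407 with factor-by-visit terms. If change is the outcome, main effects alone recover nearly all the gain (R2 0.10: 82.3% with no factors, 85.0% main effects, 85.2% by visit, all with the classical sandwich, 220 randomized and 20% lost).

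**8. Attrition.** With raw scores, 220 randomized and 20% lost at random by week 6 (8,000 trials per cell), the net change is -0.4, +1.0, +2.4 and +5.9 points; main effects alone add at most 0.6. This overstates attrition relative to the plan, whose 20% covers screening failures too.

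**The case against.** The strongest reply is that this is a preference about efficiency. The registered test is valid, no passage says that either factor predicts change, and the gain is small or absent unless they do. At R2 of 0.02 the net is about +0.2 points at N = 176, nil to -0.3 at N = 100 and about -0.6 at N = 60. A gain above 2 points at N = 176 needs each factor to shift change by more than the assumed treatment effect. The accrued sample has far more influence on power than two covariates. All of that stands, and it is why the point is minor.

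Timing also counts. Enrolment was to end in April 2024, and the cover page gives an upload date in October 2025. The documents do not say whether results by arm have been seen. The primary test has already been changed once during the trial, so a second change after unblinding would cost more in credibility than it could return in power.

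A reader might infer that leaving out balancing factors biases the comparison or invalidates the test. The documents do not support that. Allocation is random, and where the factors are prognostic the omission makes the test conservative. The 5.2% null rejection at R2 = 0 comes from the classical sandwich in a finite sample, since there the factors do nothing.

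What survives is that item 5 was asked for the exact analysis, that the factors are already recorded for allocation, and that using them costs little.

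**Conclusion.** The omission is real and its consequence is limited to precision. For R2 up to 0.10, adjusting changes power by about -0.4 to +2.5 points at 176 completers, about -1 to +2.5 at 100 and about -1.3 to +1.5 at 60; R2 of 0.20 gives about +5 and is an upper bound. These figures rest on an assumed alpha, effect size, R2, factor prevalences, urn settings and identity link, none of which the documents supply.

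A reader might also infer that adjustment would cure the power problem described in item 8. It would not: at 0.375 SD, a sample of 100 or 60 leaves power near 59% or 43%, and the factors move that by only a few points for R2 up to 0.10. This is an optional improvement.

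**What to change.** If results by arm have not been seen, add to item 5: *The primary model includes the two urn factors (parity; declining pharmacologic treatment) and their interactions with visit. Standard errors use a small-sample-corrected sandwich (Kauermann-Carroll, or n/(n - 4) scaling, counting the four parameters per visit).* If change from baseline is the outcome, use factor-by-follow-up-visit terms. Main effects alone should not be used on raw scores.

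If results by arm have been seen, keep the registered test as primary and report this model as a labelled sensitivity analysis.

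The cost is two sentences and 12 extra mean parameters on raw scores (12 to 24), or 10 on change (10 to 20). No new data are needed. If the factors are not prognostic, about 0.4 power points are lost at N = 176 and about 1 point at N = 60 to 100. The correction should accompany the factors: uncorrected, the adjusted test rejects 5.2-5.3% under the null at N = 176, 5.5-5.6% at N = 100 and 5.8-5.9% at N = 60; corrected, it rejects 5.0-5.1, 5.1-5.3 and 5.2-5.4%. Scaling by n/(n - p) with all 24 parameters over-corrects at N = 176 (null rejection 4.1-4.2%; power 76.7, 78.6, 80.6 and 84.6%) and removes the gain for R2 up to 0.10.
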